1.0 BACKGROUND AND RATIONALE

In 2016, an estimated 19,950 individuals will develop AML in the U.S.¹ With current 5-year relative survival rates of 55-60% for patients <45 years of age but only ~5% for adults >age 65 (the median age at diagnosis),² many patients will ultimately die from either treatment-related toxicities or therapeutic resistance.³⁻⁵ The need for improved therapeutic approaches is therefore unquestioned. This is particularly true for individuals presenting with medical co-morbidities that may limit their ability to tolerate intensive treatments; such patients are generally, but not invariably, older. Many of these subjects never receive any AML-directed therapy.^{6,7} Among those who do, the optimal treatment strategy is unknown but typically revolves around the choice of non-intensive therapy (e.g. azacitidine/decitabine or low-dose cytarabine) or intensive therapy (e.g. “7+3”).⁸

U.S. and European population-based registry data support the use of intensive chemotherapy rather than low-intensity therapy (or no therapy) in most AML patients up to age 80.^{6,9} Likewise, a recent retrospective analysis of 1,079 adults who received chemotherapy at 5 U.S. institutions from 2008-2012 suggested that, after adjustment for age, co-morbidity index, and cytogenetic/molecular risk, intensive therapy leads to better long-term survival even in older patients (age 70-79 years) with significant co-morbidities without increase in early mortality.¹⁰ However, these observations must be interpreted cautiously since information on exact regimens is not available and differences in supportive care and selection bias may confound the apparent benefit of intensive therapy. This possibility highlights the need for a randomized clinical trial to define the optimal treatment intensity for medically less fit AML patients with varying co-morbidity burden.

One barrier to improving care for medically less fit adults with AML has been the lack of explicit definition of “less fit”. In the AZA-001 trial, which randomized older adults with newly diagnosed AML with >30% blasts to either azacitidine or “conventional care regimens” (CCRs), i.e. best supportive care (BSC), low-dose cytarabine, or “7+3”, the investigators determined which protocol-designated CCR was most appropriate for each patient on the basis of age, performance status, and institutional practice before randomization.¹¹ Survival with azacitidine was best in those (presumably the most fit) in whom the alternative was “7+3”, and worst in those (presumably the least fit) in whom the alternative was BSC. This suggests that physicians are adept at distinguishing fit from less fit individuals. However, it seems doubtful that they are as adept as a quantitative model. To develop such a model, we recently analyzed data from 3,365 adults with newly diagnosed AML given intensive chemotherapy in SWOG trials or at M.D. Anderson Cancer Center (MDA) and found that the weekly risk of death falls sharply once 4 weeks elapse from start of intensive induction chemotherapy. This observation suggested that patients who die during this time comprise a qualitatively distinct group and allowed an empiric definition of treatment-related mortality (TRM) as deaths occurring within these 4 weeks.¹² We then used areas under the receiver operating characteristic curve (AUC) to quantify the ability of individual covariates to predict TRM in 2,238 patients treated at MDA between 1995 and 2008. Performance status (PS) and age were the most important single covariates in predicting TRM (AUC of 0.75 and 0.65 for models with PS or age alone, respectively). However, a “simplified” multicomponent model, which was validated by bootstrapping and comprised the 7 most relevant individual covariates (PS, age, platelet count, serum albumin, type of AML [secondary vs. *de novo*], white blood cell count [WBC], peripheral blood blast percentage, and serum creatinine)

led to a model with an AUC of 0.82, demonstrating an advantage of multicomponent predictive models over the use of single factors to identify the subset of patients at high risk of TRM.¹² Importantly, removal of age from this model had only a minimal effect on the AUC, suggesting that age is largely a surrogate for the other covariates contained in the model.

The TRM score, computationally derived from the “simplified” TRM model, is now in routine use at Fred Hutch, where research protocols now primarily assign patients based on predicted likelihood of TRM (e.g. NCT01342887, NCT01567059, NCT01607645, NCT01729845, NCT01804101, NCT02044796, NCT02121418, NCT02728050). Because the early death rates following intensive chemotherapy in adults with AML have declined substantially over the last 2 decades,^{13,14} we very recently re-examined the value of the “simplified” TRM model to predict early deaths in patients treated at Fred Hutch.¹⁵ Among 285 patients with newly diagnosed AML treated with intensive induction chemotherapy from 2008-2014, 17 (6.0%) died within 28 days, with the AUC of the TRM score being 0.76,¹⁵ indicating the continued value of multicomponent modeling to predict early deaths after AML therapy. So far, the comparative abilities of a model such as the one that underlies the TRM score and “physician intuition” (“I know it when I see it”) to predict TRM are uncertain. Moreover, an AUC of 0.75-0.80 approximately intermediate between certainty (AUC=1.0) and a coin flip (AUC=0.5). Therefore, although the TRM score will be the principal eligibility criterion for the pilot randomized trial, an important part of this application will be examining (a) whether incorporation of other covariates (e.g. HCT-CI, ELN risk group) will improve the ability to forecast TRM and (b) the concordance between our models and simple physician judgment. While we have developed online means to rapidly compute TRM scores (<https://cstaging.fhcrc-research.org/TRM/Default.aspx>), it is perhaps naïve to expect widespread use barring a quantitative demonstration of the value of predictive models.

Recognizing the current limitations in our knowledge regarding treatment approach to adults with AML who are medically less fit, the goal of our research, is to conduct a controlled clinical trial to improve outcomes in these patients. Because of the possibility of significant selection bias in non-randomized assessments, the preferred trial is based on a randomized assignment to higher-intensity vs. lower-intensity chemotherapy. However, such a trial may prove impractical. Therefore, this pilot study will explicitly test the feasibility of randomization in this situation, and explore reasons why patients and/or physicians might be reluctant to randomization in this situation. For this purpose, we will use preference surveys to examine patient and physician attitudes towards medical decision-making and treatment allocation. In addition to focusing on feasibility and estimates of anti-leukemia activity (e.g. response rates) and survival, we will also assess complementary dimensions of treatment benefit, in particular quality of life (QOL) as well as resource utilization and care cost.

Contemporary clinical trials often utilize DNA methyltransferase inhibitors (e.g. azacitidine or decitabine) or low doses of cytarabine as non-intensive therapy, whereas multi-agent chemotherapy, most typically in the classic 7+3 combination between cytarabine and an anthracycline as intensive therapy. However, treatment outcomes with standard therapeutics in medically less fit individuals with AML are relatively poor. This is exemplified by the AZA-001 trial, in which median overall survival times of approximately 6-7 months for low-dose cytarabine and 10-12 months for azacitidine or 7+3 were estimated. This observation highlights the need for better therapies. In a recent phase 1/2 trial in medically fit adults with newly diagnosed AML, we found that combination therapy with G-CSF, cladribine, high-dose cytarabine, and escalated doses of mitoxantrone (G-CLAM) is well tolerated and appears to produce higher rates

of CR, CR without MRD, and possibly longer survival than 7+3, after accounting for prognostic covariates. Given these data, G-CLAM will be used as intensive therapy in our pilot trial (“higher-dose G-CLAM”). As comparator non-intensive therapy, we will use G-CLAM with reduced doses of cladribine, cytarabine, and mitoxantrone (“lower-dose G-CLAM”). Rather than selecting different classes for the non-intensive and intensive treatment arm in our trial – which may have different modes of action and therefore confound the question of treatment intensity – we purposefully chose G-CLAM as backbone for both arms.

Development of G-CLAM as highly active, intensive chemotherapy for newly diagnosed AML

Since 2012, we have used G-CLAM extensively in adults with newly diagnosed AML and high-grade MDS, primarily as part of a large, ongoing institutional phase 1/2 trial (FHCRC #2734.00). Our interest in this regimen stems from data indicating improved anti-leukemic activity with regimens containing cladribine, high-dose cytarabine, and escalated doses of mitoxantrone compared to standard 7+3 chemotherapy. Data from this trial, which was presented at the 2016 annual meeting of the American Society of Hematology, have established the safety of a G-CLAM regimen with escalated doses of mitoxantrone, which will form the basis for the backbone used in this proposal. Specifically, the phase 1 portion on 33 patients established the highest dose tested (mitoxantrone at 18 mg/m²/day) as the maximally tolerated dose. A total of 62 patients, including 6 treated in phase 1, received G-CLAM at MTD. Patient characteristics were as follows: median age 58 (21-81) years, median TRM score 2.85 (0.06-6.73), with AML (n=52) or high-risk MDS (n=10). Cytogenetics were favorable in 6, intermediate in 44, and adverse in 12 (MRC criteria); 11 patients had NPM1 and 6 had FLT3 mutations. Fifty-two patients (83.9%, 95% confidence interval: 72.3-92.0%) achieved a CR (n=48 [77.4%: 65.0-87.1%]), or CRp/i (n=4 [6.5%: 1.8-15.7%]) with 1-2 cycles of therapy. Only 3 patients required 2 cycles to best response. Among the 48 CR patients, 43 (89.6%) were negative for measurable residual disease (MRD^{neg}) by flow cytometry. Four patients had morphologic leukemia free state, 1 patient with myeloid sarcoma had a partial remission, 4 had resistant disease, and 1 died from indeterminate cause. One patient died within 28 days of treatment initiation (septic shock). Median times to an absolute neutrophil count \geq 500/ μ L and a platelet count of \geq 50,000/ μ L were 26 and 23 days. Besides infections and neutropenic fever, maculopapular rash, and hypoxia (fluid overload/infection-related) were the most common grade \geq 3 adverse events. In addition to the phase 1/2 MTD cohort, there were 15 patients treated in an expansion cohort and 3 eligible patients treated off protocol with mitoxantrone at 18 mg/m². For these 80 patients combined treated at MTD, the CR and CR/CRp/i rates were 76.3% and 81.2%. After multivariable adjustment, compared to 300 patients treated with 7+3 on the SWOG S0106 trial, G-CLAM with mitoxantrone 18mg/ m² was associated with an increased probability of CR (odds ratio [OR]= 3.08, p=.02), CR/CRp/i (OR=2.96, p=.03), a trend towards improved MRD^{neg} CR (OR= 3.70, p=.06), and a trend towards improved overall survival ([OS]; hazard ratio=0.34, p=.07). For the entire study cohort, the 6 and 12-month relapse-free survival were 73% (64-83%) and 62% (42-74%) and the 6 and 12-month OS were 89% (82- 96%) and 77% (67-88%). Together, our study found G-CLAM with mitoxantrone up to 18 mg/m²/day to be well tolerated and to have potent anti-leukemia activity.

In this pilot study, patients meeting the in/exclusion criteria and primary oncologists are asked whether or not they would agree to participate in the randomized treatment assignment. Patients agreeable to randomization will be assigned in a 1:1 ratio to the higher-intensity arm and given G-CLAM or the lower-intensity arm that is built on G-CLAM but utilizes lower doses of

cladribine, cytarabine, and mitoxantrone. For the other patients, the reasons to decline randomization will be recorded, and patients will be allowed to receive the treatment intensity of their choosing. We will then follow these patient for a variety of disease specific outcomes—remission rates, overall survival—as well as examine patient and physician attitudes towards medical decision-making and treatment allocation, assess QOL, and examine resource utilization and care cost.

2.0 OBJECTIVES

2.1 Primary Objective

- 2.1.1 To evaluate the feasibility of randomizing medically less fit adults with newly diagnosed AML or analogous myeloid neoplasms to either intensive or non-intensive induction and post remission chemotherapy.

2.2 Exploratory Objectives

- 2.2.1 To evaluate the attitude of patients and physicians toward randomization and explore reasons for treatment preference.
- 2.2.2 To evaluate whether the ability to assess fitness for intensive chemotherapy can be improved by an augmented treatment-related mortality (TRM) score that includes additional (co-morbidity) factors, and to compare the ability of physicians and the prediction algorithm(s) to assess the likelihood of early death.
- 2.2.3 To compare, within the limits of a pilot study, response, duration of response, and survival between patients receiving intensive and those receiving non-intensive chemotherapy.
- 2.2.4 To describe the impact of treatment intensity on quality of life of patients undergoing chemotherapy for newly diagnosed AML.
- 2.2.5 To describe the impact of treatment intensity on medical resource utilization and care cost of patients undergoing chemotherapy for newly diagnosed AML.

3.0 PATIENT ELIGIBILITY

3.1 Inclusion Criteria

- 3.1.1 Age ≥ 18 years
- 3.1.2 Diagnosis of untreated “high-grade” myeloid neoplasm ($\geq 10\%$ myeloid blasts by morphology in bone marrow and/or peripheral blood) or AML other than acute promyelocytic leukemia (APL) with t(15;17)(q22;q12) or variants according to the 2016 WHO classification.¹⁶ Patients with acute leukemias of ambiguous lineage are eligible. Outside diagnostic material is acceptable as long as peripheral blood and/or bone marrow slides are reviewed at the study institution and cytogenetic/molecular information is available.

- 3.1.3** Treatment-related mortality (TRM) score ≥ 13.1 as calculated with simplified model (see APPENDIX A).¹²
- 3.1.4** The use of hydroxyurea before enrollment is permitted; hydroxyurea should be discontinued prior to start of study treatment. Patients with symptoms/signs of leukostasis, WBC $>100,000/\mu\text{L}$, or acute symptoms felt related to their high-grade myeloid neoplasm can be treated with leukapheresis or may receive up to 1 dose of cytarabine (up to 500 mg/m²) anytime prior to study day 1.
- 3.1.5** Patients may have received treatment (e.g. azacitidine/decitabine, lenalidomide, growth factors) for antecedent low-grade myeloid neoplasm.
- 3.1.6** Left ventricular ejection fraction (LVEF) $\geq 45\%$, assessed within 3 months prior to registration, e.g. by MUGA scan or echocardiography, or other appropriate diagnostic modality.
- 3.1.7** Women of childbearing potential and men must agree to use adequate contraception beginning at the signing of the consent until at least 4 weeks after the last dose of study drug.
- 3.1.8** Ability to understand and the willingness to sign a written informed consent document

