4.0 EVALUATION AND COUNSELING OF PATIENT

The patient will be completely evaluated with a history, physical examination, diagnostic testing if necessary, and review of outside slides and records if available. The protocol will be discussed thoroughly with the patient and family (if present), with description of all known risks to the patient. Alternative forms of treatment will be presented as objectively as possible, and the risks and hazards of the study explained to the patient. Consent will be obtained using forms approved by the local Institutional Review Board (IRB).

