6.0 TREATMENT PLAN

This study is a single-center, open-label randomized pilot study of lower-dose vs higher-dose G-CLAM for medically less fit adults with newly diagnosed AML or analogous myeloid neoplasms at the Fred Hutchinson Cancer Research Center/University of Washington/Seattle Cancer Care Alliance.

Study Overview

In this pilot study, patients meeting the inclusion/exclusion criteria and their primary oncologists are asked whether or not they would agree to participate in the randomized treatment assignment (APPENDIX D). Patients agreeable to randomization will be assigned in a 1:1 ratio to the higher-dose G-CLAM arm or the lower-dose G-CLAM arm that utilizes lower doses of cladribine, cytarabine, and mitoxantrone. For those who wish to not be randomized, the reasons to decline randomization will be recorded, and patients will be allowed to receive the treatment intensity of their choosing. Patients will receive higher-dose or lower-dose G-CLAM as follows:

Treatment arm	G-CSF (SC, D0-D5)	Cladribine (IV 2h, D1-D5)	Cytarabine (IV, D1-D5)	Mitoxantrone (IV, D1-D3)
Higher-dose G-CLAM	300 or 480 µg*	5 mg/m ²	2,000 mg/m ² **	18 mg/m ²
Lower-dose G-CLAM	300 or 480 µg*	2 mg/m ²	100 mg/m ² ***	6 mg/m ²

*Dosing based on patient weight: <76kg vs. ≥76 kg; **over 2 hours; ***over 1 hour

After study enrollment, patients will receive a first cycle of G-CLAM on one of the designated treatment arms. Post-induction bone marrows will be reassessed upon blood count recovery or between day Days +28 to +35 after start of chemotherapy, whichever occurs first. If a response other than a measurable (“minimal”) residual disease-negative (MRDneg) CR is achieved, the patient will receive re-induction with G-CLAM at the same dosing. Patients who achieve a morphologic CR or CR with incomplete count recovery (CRi) with up to 2 courses of higher-dose G-CLAM or up to 6 courses of lower-dose G-CLAM can receive consolidation therapy with G-CLA (i.e. mitoxantrone omitted; up to 4 cycles with high-dose G-CLA and up to 12 cycles of low-dose G-CLA).

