6.6 Consolidation Therapy

After achievement of a CR/CRI (irrespective of MRD) with 1-2 courses of G-CLAM therapy, patients are eligible for post-remission therapy with G-CLA.

- 6.6.1 The treatment is identical to the induction course but without mitoxantrone (i.e. G-CSF, cladribine, and cytarabine, or “G-CLA” at same dose level as induction). If a patient had excessive toxicities (grade ≥ 3 non-hematologic toxicity excluding neutropenic fever and infections) during induction, a dose reduction can be considered as described in sections 6.8 and 6.9, as well as APPENDIX B.
- 6.6.2 Post-remission courses should start within 6 weeks of achieving CR/CRI once patients have recovered to \leq Grade 2 toxicities from the previous course of therapy.
- 6.6.3 Patients on the higher-dose arm can receive up to 4 courses of consolidation therapy.
- 6.6.4 Patients on the lower-dose arm can receive up to 12 cycles of consolidation therapy.
- 6.6.5 Patients can proceed to transplantation barring contraindications and if a suitable donor is available.

6.7 **Monitoring during/after Induction and Consolidation Therapy**

For patient monitoring, the following studies and study intervals are suggested and will be performed at the physician's discretion:

- 6.7.1 Complete blood counts with differential blood count, including immature cells/blast, and platelet count at least 2 times weekly until ANC >500/ μ L and then at least weekly until platelet count >100,000/ μ L.
- 6.7.2 Metabolic panel, including bilirubin, ALT/AST, and creatinine at least weekly until ANC >1,000/ μ L and platelet count >100,000/ μ L.
- 6.7.3 If patients develop signs or symptoms suggestive of cardiac dysfunction, LVEF should be assessed using the same method to evaluate baseline LVEF status (MUGA scan or echocardiography, or other appropriate diagnostic modality).

6.8 **Dose Modifications of Chemotherapeutic Drugs for Induction or Subsequent Treatment Cycles for Higher-Dose Arm**

For patients who have organ dysfunction at baseline—defined as a serum creatinine > 2.0 mg/dL or a bilirubin concentration is $\geq 3 \times$ IULN— or those who experienced \geq Grade 3 non-hematologic toxicities excluding neutropenic fever and infections during the first induction, a dose reduction can be considered as follows (see also APPENDIX B):

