7.3.5 Administration and Compatibility: The diluted cytarabine solution should be inspected for particulate matter, discoloration, and haze prior to infusion. If there is evidence of particulate matter, discoloration, or haze the solution should not be infused. Patients should be medicated with standard anti-emetic therapy. Cytarabine is not compatible (1) during Y-site administration with allopurinol, amphotericin B, ganciclovir; (2) in syringe with metoclopropamide; or (3) admixed with fluorouracil, heparin, insulin (regular), nafcillin, oxacillin, penicillin G. Cytarabine may have variable compatibility when admixed with gentamycin, hydrocortisone, and methylprednisolone.

7.3.6 Storage and Stability: Vials of non-reconstituted cytarabine should be stored at room temperature 15°C - 30°C (59°F - 86°F). The diluted cytarabine solution may be stable for up to 48 hours if stored at room temperature.

7.3.7 Drug-Drug Interaction: Reversible decreases in the plasma steady-state concentration for digoxin and cardiac glycosides may occur. Cytarabine may diminish the therapeutic effect of flucytosine. There is *ex vivo* data suggesting that cytarabine may reduce the effectiveness gentamycin for killing *K. pneumoniae*.

7.3.8 Warnings and Precautions: *Ex vivo* and *in vivo* studies have found that cytarabine causes extensive chromosomal damage and potential malignant transformation. Although there have been some case reports describing cytarabine use in pregnant humans, these cases reports are few. Thus, cytarabine is considered Pregnancy Category D. Women should be advised not to become pregnant while receiving cytarabine, and men should be advised not to father a child while receiving cytarabine and for at least 3 months after completing the therapy. It is not known whether cytarabine or its metabolites are excreted in breast milk; thus, it is not recommended for lactating females who are breast-feeding. As with any highly immunosuppressive medication, cytarabine may diminish the effectiveness of dead and live vaccines and enhance the toxic/adverse effect of live vaccines. One should avoid use of live vaccines while receiving it. A small percentage of patients will have a hypersensitivity reaction to cytarabine, and these individuals should not receive the drug again.

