14.5 Ethnic and Gender Distribution Chart

All eligible patients will be included in this study without regard to gender or ethnicity. The incidence of AML is slightly higher in men, so it is expected that the distribution of these patients will reflect a slight male predominance of the disease as well as the general demographic distribution of AML patients seen at our institution. Up to 50 patients with newly diagnosed AML or analogous high-grade neoplasms will be enrolled in this study.

Projected Target Accrual
ETHNIC AND GENDER DISTRIBUTION CHART

TARGETED / PLANNED ENROLLMENT: Number of Subjects			
Ethnic Category	Sex / Gender		
	Females	Males	Total
Hispanic or Latino	1	1	2
Not Hispanic or Latino	20	28	48
Ethnic Category Total of All Subjects*	21	29	50
Racial Categories			
American Indian / Alaska Native	0	0	0
Asian	1	1	2

Native Hawaiian or Other Pacific	0	0	0
Black or African American	1	1	2
White	19	27	46
More Than One Race	0	0	0
Racial Categories: Total of All	21	29	50

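### Criterion 3.1.7 asks men for contraception until only 4 weeks after the last dose, while the protocol's own cytarabine precaution in 7.3.8 advises 3 months

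*Combined protocol and SAP*

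**What the plan says.** Section 3.1.7 (Inclusion Criteria) states one rule for both sexes: "Women of childbearing potential and men must agree to use adequate contraception", starting when consent is signed and continuing "until at least 4 weeks after the last dose of study drug". Women are included only if of childbearing potential; men are included without restriction.

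Section 7.3.8 (Warnings and Precautions for cytarabine) gives a different period for men: "men should be advised not to father a child while receiving cytarabine and for at least 3 months after completing the therapy". The same paragraph opens by reporting study evidence that "cytarabine causes extensive chromosomal damage and potential malignant transformation". It gives no post-treatment period for women.

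The dosing table in section 6.0 has a cytarabine column that applies to both arms, headed "Cytarabine (IV, D1-D5)". Section 6.6.1 says of consolidation: "The treatment is identical to the induction course but without mitoxantrone". Cytarabine is therefore in every course a patient can receive.

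Section 4.0 requires the protocol to be discussed with the patient "with description of all known risks to the patient". It gives no contraception period.

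**The concern.** An eligibility criterion defines what is sufficient for entry. On contraception, 3.1.7 is the commitment that staff check at enrolment, and for men it is shorter than the protocol's own safety advice about a drug that all of them receive. A man who stops contraception in week 5 has met the entry rule in full, yet he is about two months short of what 7.3.8 says he should be told.

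What is at stake is participant safety, including that of a partner and a possible child, and the internal consistency of the protocol. Staff who work from the eligibility list could reasonably tell men 4 weeks. The point has no bearing on the primary endpoint, the sample size, the stopping rules or any analysis.

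**Working it through.** The plan gives no calculated figure to reproduce. The check compares the two periods and asks whether they start on the same day.

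**Inputs**

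- Entry minimum for men: 4 weeks after the last dose of any study drug (3.1.7).
- Advised minimum for men: 3 months after completing cytarabine (7.3.8).
- Last scheduled day of each drug in an induction course, the same on both arms (6.0, 6.3, 6.4): G-CSF Day 5, cladribine Day 5, cytarabine Day 5, mitoxantrone Day 3.
- Consolidation omits mitoxantrone only (6.6.1), so cytarabine again ends on Day 5.
- Projected enrolment: 29 men among 50 patients (chart in 14.5).

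**Step 1: do the two periods start together?** The 3.1.7 period starts at the last dose of any study drug, and the 7.3.8 period at the end of cytarabine. No scheduled drug continues past Day 5, and cytarabine is itself given on Day 5. As scheduled, both periods therefore start on Day 5 of the last course, whichever arm the man is on and whether that course is induction or consolidation. The order of the drugs does not narrow the gap.

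**Step 2: the length of the gap**

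- 4 weeks = 4 × 7 = 28 days.
- 3 calendar months = 89 to 92 days, depending on the start date.
- Gap = 89 − 28 = 61 days to 92 − 28 = 64 days.
- In weeks: 61/7 = 8.7 to 64/7 = 9.1.
- Share of the advised period that the entry rule covers: 28/92 = 30% to 28/89 = 31%.

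**Step 3: could departures from the schedule close the gap?**

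- Missed doses are not made up (6.3.4, 6.4.4). If a man received cytarabine on Day 1 only but another study drug through Day 5, the starting points would differ by 5 − 1 = 4 days, leaving at least 61 − 4 = 57 days.
- Section 6.10.2 allows additional growth factors as supportive care. The protocol does not say whether later G-CSF would count as study drug. If it did, it would have to continue for about 61 to 64 days beyond Day 5 to close the gap.

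**Step 4: who is covered?** The criterion applies to all men, a projected 29/50 = 58% of enrolment. This is a planning figure. The number of men for whom the gap matters in practice is not given and could be anywhere from 0 to 29.

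**Step 5: is there a reconciling statement?** No section available for review gives men a longer period or says which of the two governs.

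**The case against.** The strongest reply is that the two statements do not contradict each other. Both are minimums; 3.1.7 is an entry commitment and 7.3.8 is advice. A man who follows the advice satisfies both. Counselling should deliver that advice: section 4.0 requires the known risks to be described, section 16.3 requires a full explanation of the treatment before consent, and 7.3.8 is itself an instruction to advise men. The consent form, where the period would normally be stated, was not available, so no man can be shown to have been told the wrong thing. Many of these patients will be older, and the number affected may be small. A cross-reference to 7.3.8 might be enough, without turning advice into an eligibility bar.

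Much of this stands. The periods are compatible, what men are actually told cannot be judged here, and the practical number may be as low as zero. It is also fair to say that 7.3.8 does not expressly give chromosomal damage as the reason for the 3-month interval; the two appear in the same paragraph and the link is an inference. The mismatch does not depend on that link.

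The reply does not remove the mismatch itself. Sections 4.0 and 16.3 name no period, so they do not override the one in 3.1.7. If the consent form already says 3 months, 3.1.7 disagrees with it and still needs aligning. Age is not a full answer either: eligibility starts at 18, and section 1.0 notes that less fit patients are not always older. The sponsor judged contraception in men important enough for an entry criterion, so its length should not fall short of the sponsor's own advice.

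**Conclusion.** The concern holds. For men, the entry minimum in 3.1.7 ends 61 to 64 days before the period advised in 7.3.8 and covers about 30% to 31% of it, on either arm. The size assumes that treatment ends on Day 5 of the last course as scheduled and that 3 months means calendar months; plausible departures change it by days.

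This is a participant-safety inconsistency that should be corrected. It is not a flaw in the statistical design. The mismatch in the text is certain. Whether any man has been or would be misinformed is not known, because it depends on the consent form and on counselling. The mismatch concerns men only, since 7.3.8 sets no post-treatment period for women.

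**What to change.** Split 3.1.7 by sex. Women of childbearing potential keep the present commitment, from consent until at least 4 weeks after the last dose of study drug. Men commit from consent until at least 3 months after the last dose of study drug. Counting from the last dose of any study drug meets 7.3.8 whichever drug happens to be given last. Then confirm that the consent form gives men the same 3 months.

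The cost is one amended sentence and a check of the consent wording, with no statistical cost. The one downside is that a man unwilling to commit to 3 months would no longer be eligible.
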